## **Study Protocol, Statistical Analysis, and Results**

### **Study Protocol**

Participants who responded to invitations to voluntarily participate completed the Physical Activity Readiness Questionnaire (PAR-Q+) (Warburton et al. 2011), followed by a questionnaire to rate their current stage of change (SOC) from the Transtheoretical Model adapted to assess exercise/postural modification behavior change. On this questionnaire, participants also responded to a yes/no question regarding if they have had a recent injury to their head, shoulders, or spine; or have ever been diagnosed with a pathology related to their cervical/thoracic spine or extremities, as part of exclusion criteria for the study. Participants then underwent a head posture screening with the use of photogrammetry. Screening was performed by the primary investigator who is a licensed physical therapist in the Liberty University Biomechanics & Motion Analysis Laboratory.

Participants were asked to arrive at the lab wearing either a tank top or t-shirt, as well as to have their hair tied back if necessary. Height and weight were measured using a digital scale (Health-o-meter Professional, model 500KL, McCook, IL). Participants were instructed to sit comfortably on a stool with hands resting approximately two-thirds down their thighs with palms supinated and feet flat on the ground with hips and knees at 90 degrees (Richards et al. 2016); and to look straight ahead at an opposite wall in the laboratory (Kim et al. 2016). A digital camera (Canon Powershot, model SX540, Tokyo, Japan) was mounted and leveled on a tripod (Manfrotto, model 055, Cassola, IT) and placed three meters away from the subject (Ruivo et al. 2014). Two photographs were taken of participant's posture (Kim et al. 2016). Immediately after data capture, image files were uploaded into Kinovea video analysis software (version 8.15) for CVA assessment. On each image file, the PI assessed participant CVA by measuring the angle

between the intersection of two lines: the first line drawn from the tragus of the ear to the spinous process of C7 vertebrae and the second line drawn horizontally through C7 spinous process (Kim et al. 2016). A second researcher directly observed the PI perform each CVA assessment, as well as provided verbal agreement with the accuracy of angle measurement. For each participant, the CVA was derived by taking the mean of two CVA measurements that were assessed on the captured photographs (Kim et al. 2016).

Inclusion criteria included completion of informed consent, craniovertebral angle  $\leq 53$  degrees (Lee et al. 2017) and self-rating of Transtheoretical Model stage of change stage  $\geq 3/5$  on a questionnaire to indicate their readiness to comply with an assigned exercise prescription or postural guidelines (Kuroda et al. 2012). Exclusion criteria consisted of any musculoskeletal injury to the head, shoulders, or spine within the last six months; diagnosis of pathology related to the cervical spine, thoracic spine, or upper extremities; or non-clearance for physical activity based on results of the PAR-Q+ questionnaire. A total of 79 participants met inclusion criteria and were included in the study.

Randomization of participant group assignments was completed by the PI using a block randomization generator on a website (<http://www.randomization.com>). Utilizing a sequence created by the block randomizer, the PI placed participants who met inclusion criteria into one of four groups: (PE; n = 20), self-myofascial release + stretching (SMRS; n = 20), self-myofascial release + stretching + strengthening (SMRSS; n = 19), and control group (CG; n = 20). A hard-copy of the sequence generator report was kept concealed in a manila folder and was only opened by the PI during group delegation. Participants and researchers were not blinded to group assignment.

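### The allocation list was not concealed from the PI, who enrolled participants and read the angle that sets both eligibility and baseline

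*Combined protocol and SAP*

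**What the plan says.** All of the relevant text on roles is in the Study Protocol section.

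- **Screening:** "Screening was performed by the primary investigator".
- **Reading:** "On each image file, the PI assessed participant CVA by measuring the angle", with lines placed by hand in video-analysis software. The CVA used is the mean of the readings on two photographs.
- **Entry:** one inclusion criterion is "craniovertebral angle $\leq 53$ degrees".
- **Sequence:** "Randomization of participant group assignments was completed by the PI using a block randomization generator on a website". Block size is not stated.
- **Assignment:** "the PI placed participants who met inclusion criteria into one of four groups".
- **Custody:** "A hard-copy of the sequence generator report was kept concealed in a manila folder and was only opened by the PI during group delegation".
- **Check on the reading:** "A second researcher directly observed the PI perform each CVA assessment, as well as provided verbal agreement with the accuracy of angle measurement".

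The same section states that neither participants nor researchers were blinded. Under Intervention Groups, each arm's training session, or the notice of no intervention, comes immediately after the baseline assessment. Only one CVA assessment before the intervention is described, so the screening value is also the baseline value. Under Statistical Analysis, the arms are compared on CVA change by one-way ANOVA, with no adjustment for baseline.

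**The concern.** Allocation concealment means that whoever decides entry cannot know the next assignment when making that decision. A folder that is closed to everyone except the enrolling investigator does not provide this. Here the PI had seen the sequence at generation or could see it whenever the report was opened. The same PI then made a manual reading that determined whether the next person entered and at what baseline.

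Two biases become possible, and they act differently.

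- **Baseline misreading.** If baseline is read a little low when an exercise arm is next, the shortfall is subtracted in the change score and reappears as apparent improvement. Masking the follow-up reading would not remove it.
- **Selective entry.** A person near 53 degrees can be read in or out according to the next arm. This can alter who is in each arm, but it does not pass one for one into the change contrast, because the person's true angle is in both the pre and the post value.

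Calling the list concealed also leads a reader to credit the trial with a safeguard that it did not have against the person for whom it matters.

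**Working it through.** **1. Arm counts.** 20 + 20 + 19 + 20 = 79, which matches the stated total. The documents give no power calculation to reproduce.

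**2. Roles.** Five functions belong to the PI: generating the sequence, holding and opening the list, screening, reading the CVA, and placing participants in groups. The text implies an order (eligibility first, then assignment). It does not say that the reading was written down or locked before the folder was opened, that only one assignment was visible at a time, or that the PI was kept from seeing the sequence when it was generated.

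**3. Effect of a baseline misreading.** Change = post − baseline. If baseline in one arm is read d degrees too low relative to control, the contrast rises by d. From the Results section:

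- SMRS − CG = 3.8 − 0.8 = 3.0 degrees
- SMRSS − CG = 4.4 − 0.8 = 3.6 degrees

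For scale, d = 1 would be 1/3.0 = 33% and 1/3.6 = 28% of these. The 1 degree is illustrative; nothing in the documents gives a size for d.

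**4. How much d would matter to the significance claims.** Assumptions: 18 completers per arm (72/4; completers by arm are not given), a PE change SD of 1.7 to 3.3 (not given), and a Sidak adjustment for six comparisons as a stand-in for Gabriel's test.

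- With PE SD 2.5, the pooled variance is (3.3² + 3.1² + 1.7² + 2.5²)/4 = 7.41.
- SE = √(7.41 × 2/18) = 0.907, and the critical t on 68 degrees of freedom is 2.71.
- Margin for SMRS: 3.0 − 2.71 × 0.907 = 0.54 degrees. Margin for SMRSS: 3.6 − 2.71 × 0.907 = 1.14 degrees.
- Over the PE SD range, the margins are about 0.4 to 0.7 degrees (SMRS) and 1.0 to 1.3 degrees (SMRSS). With 17 to 20 per arm they widen to 0.3 to 0.8 and 0.9 to 1.4 degrees.

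These are sensitivity figures, not estimates of bias.

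**5. What the baseline comparison can rule out.** Results reports no significant difference in baseline CVA. The baseline SD is not given; assume 3 to 5 degrees, with 18 per arm. The SE of a two-arm difference is SD × √(2/18), and power is for a two-sided 5% t-test.

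| Assumed baseline SD | SE of difference | Power for a 1-degree tilt | Power for a 3-degree tilt |
|---|---|---|---|
| 3 | 1.0 | 16% | 83% |
| 5 | 1.67 | 9% | 42% |

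**6. Predictability without the list.** In a four-arm block of size b = 4m, the expected share of assignments that are certain from the preceding ones is 1/(3m + 1).

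| Block size | Certain assignments |
|---|---|
| 4 | 1/4 = 25% |
| 8 | 1/7 = 14% |
| 20 | 1/16 = 6% |
| 80 | 1/61 = 1.6% |

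The 20/20/19/20 split fits every multiple of four from 4 to 80, so it does not identify the block size.

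**The case against.** The strongest reply is that the protocol contains safeguards. A second researcher watched every reading and agreed it aloud, so a deliberately shifted line would have to pass a witness each time. The CVA averages two photographs. The text says that the folder was opened only at delegation, and it describes those assigned as people who already met the criteria.

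Most of this stands as partial protection. It does not close the gap. The observer is not stated to be masked or to measure independently, and has no described control over the list. Averaging two photographs reduces random error, but not an error in a consistent direction. Opening the folder only at delegation does not stop the person who created the sequence, or who saw the report on an earlier opening, from knowing what comes next.

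Three stronger readings are tempting, and the documents do not support them.

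- **That the list was open, or that the PI in fact foresaw each assignment.** The text says it was kept from others and opened at delegation. The layout of the report and the way it was consulted are not described.
- **That blocks of four were used, so a quarter of assignments were certain.** The arm counts cannot show this.
- **That bias occurred or explains the result.** No document gives evidence of it. The baseline comparison also carries some information against a tilt as large as the whole effect: under the assumptions above, it would detect 3 degrees 42% to 83% of the time.

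It is also fair that the roles and the lack of blinding are openly disclosed.

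**Conclusion.** The concern holds in a limited form and should be fixed. Allocation was not concealed from the enrolling assessor, and that assessor hand-read the single value that serves as both entry criterion and baseline. No described step fixes that value before the next arm can be known. This follows from the text and needs no numerical assumption.

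The size of any bias is unknown. A baseline misreading of d degrees that differs by arm shifts contrasts of 3.0 and 3.6 degrees by d; selective entry does not act in this way. The non-significant baseline comparison is weak reassurance about tilts near 1 degree, given an assumed SD of 3 to 5 degrees and 18 per arm. Between 1.6% and 25% of assignments would be certain without the list, depending on a block size that is not stated. Confidence is high for the overlap of roles, but does not extend to the presence or size of bias.

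**What to change.** **For any continuation or repeat.** In the randomization paragraph of the Study Protocol section, assign generation and custody of the sequence to an existing team member who neither screens nor reads CVA. That person releases one assignment at a time, and only after the PI has recorded and locked the CVA readings and the eligibility decision. The cost is small: custody moves among existing staff, and that person must be reachable at each enrolment.

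**For the completed trial.** The custody change cannot be applied in retrospect. Replace the description of the list as concealed with a statement that allocation was not concealed from the enrolling assessor, and report this as a limitation. This costs one or two sentences.

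**If the records exist.** The documents mention no screening log, enrolment order, or CVAs of people excluded. If enrolment order and screening CVAs were retained, compare entry decisions near 53 degrees with the arm that was next on the printed list. If the baseline photographs were retained, a masked re-reading would test for baseline misreading directly.

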### ***Questionnaires and Follow-up Posture Assessment***

Two weeks into the study, participants assigned to intervention groups completed a mid-study questionnaire to assess intervention compliance. After the completion of 4-week intervention period, participants in the intervention groups completed a post-study questionnaire to assess intervention compliance and participants in all groups were asked to return to the Biomechanics laboratory to undergo a follow-up posture assessment.

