### **Statistical Analysis**

Data were analyzed using IBM SPSS version 28 for Windows (SPSS Inc., Chicago, IL, USA) and reported with mean and standard deviation. Descriptive participant characteristics by group were analyzed with a one-way ANOVA. Paired samples *t*-tests were used to assess within-group differences in means between pre- and post-intervention CVA measures. Between-group comparisons of post-intervention mean CVA change were analyzed with a one-way ANOVA. Levene's test was utilized to assess equality of error variance. Gabriel's test was selected for post-hoc comparisons. The significance level was set at  $p < 0.05$ .

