## **Results**

The trial was completed by 72 participants (51 females, 21 males) with a mean age: 20.17 (SD:  $\pm 2.25$  years); mean height: 167.34 (SD:  $\pm 8.25$  cm); and mean weight: 70.31 (SD:  $\pm 14.61$  kg). All participants reported SOC self-rating  $\geq 3/5$ . Pre-intervention analysis revealed no significant difference ( $p > 0.05$ ) in participant age or anthropometric characteristics between groups. No significant between-group differences ( $p > 0.05$ ) in baseline CVA were present. Within-group comparisons of pre- vs post-intervention CVA outcomes revealed a significantly ( $p < 0.05$ ) greater post-intervention CVA in the PE, SMRS, SMRSS, and CG. Post-hoc comparisons indicated post-intervention mean CVA change in the SMRS group: 3.8 (SD:  $\pm 3.3$  deg.); and the SMRSS group: 4.4 (SD:  $\pm 3.1$  deg.); was significantly greater ( $p < 0.01$ ) than the CG: 0.8 (SD:  $\pm 1.7$  deg.). All participants in the SMRS and SMRSS groups reported intervention adherence as moderately consistent (50-75% sessions performed) or higher on both the mid- and post-study questionnaire. 91% of the PE group reported intervention adherence as moderately consistent (50-75% adherence to guidelines) or higher on the mid-study questionnaire. 96% of the PE group reported intervention adherence as moderately consistent or higher on the post-study questionnaire.

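### Craniovertebral angle (CVA), the only outcome tested between groups, is read by hand by an unblinded reader, and watch-and-agree is not an adequate check on follow-up reading error that differs by arm

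*Combined protocol and SAP*

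**What the plan says.** All on this point comes from the combined protocol and SAP.

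- **Reading (Study Protocol).** Two photographs are taken, and "Immediately after data capture, image files were uploaded into Kinovea video analysis software". Then "On each image file, the PI assessed participant CVA by measuring the angle" between a line from the tragus to C7 and a horizontal line through C7.
- **Replication (Study Protocol).** For each participant "the CVA was derived by taking the mean of two CVA measurements that were assessed on the captured photographs".
- **Check (Study Protocol).** "A second researcher directly observed the PI perform each CVA assessment, as well as provided verbal agreement with the accuracy of angle measurement".
- **Masking (Study Protocol).** "Participants and researchers were not blinded to group assignment".
- **Follow-up (Questionnaires and Follow-up Posture Assessment).** After four weeks "participants in all groups were asked to return to the Biomechanics laboratory to undergo a follow-up posture assessment". The section names no reader and mentions no coded images, reading order or second reading.
- **Analysis (Statistical Analysis).** Mean CVA change is compared between groups by one-way ANOVA, and Gabriel's "test was selected for post-hoc comparisons".
- **Result (Results).** "Post-hoc comparisons indicated post-intervention mean CVA change in the SMRS group" (3.8, SD 3.3 degrees) and in the SMRSS group (4.4, SD 3.1) exceeded that in the control group (0.8, SD 1.7), with p < 0.01.

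No intra-reader or inter-reader agreement figure is planned or reported.

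**The concern.** Placing a line through the tragus and C7 on a photograph takes judgement, and a reader who knows the arm can lean in one direction without intending to. The exposure lies mainly at follow-up: the baseline reading decides eligibility and comes before participants receive their intervention or are told that they are controls.

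The safeguards in the protocol address other problems. Standard seating, a levelled camera at three metres and the mean of two photographs reduce random error, but they leave a lean shared by both photographs untouched. The second researcher sees the lines already drawn, is covered by the same non-blinding statement, and has no separate value described.

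Participants cannot be masked to exercise, but the reader of a stored photograph can be. What is at stake is the main finding: the two significant contrasts with control both rest on this reading.

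**Working it through.** **1. How reading error enters.** With mean follow-up reading error b in each arm, observed difference = true difference + (b in exercise arm − b in control arm). Error common to all arms cancels. Differential error adds one for one, and the p-value cannot separate it from effect.

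**2. Error needed to explain everything.**
- SMRS − control: 3.8 − 0.8 = 3.0 degrees.
- SMRSS − control: 4.4 − 0.8 = 3.6 degrees.

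**3. Inputs for the fragility check.** The means and SDs are those in Results. The documents do not give completers per arm or the PE standard deviation. I assume 72 / 4 = 18 completers per arm, that the reported p < 0.01 is the Gabriel p-value, and two-sided testing. The PE SD is varied upward from 1.7, the smallest SD reported.

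**4. Reproducing the reported p < 0.01.** At 18 per arm, Gabriel's critical difference is m × s × 2/√36 = m × s/3. Here s is the pooled SD, and m is the studentized maximum modulus for six comparisons and 72 − 4 = 68 degrees of freedom: 2.706 at 0.05 and 3.272 at 0.01. The pooled SD is s = √[(3.3² + 3.1² + 1.7² + PE SD²)/4].

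| PE SD | s | Critical difference at 0.05 | p, SMRS−control | p, SMRSS−control |
|---|---|---|---|---|
| 1.7 | 2.563 | 2.31 | 0.005 | 0.0005 |
| 2.62 | 2.750 | 2.48 | 0.010 | 0.0012 |
| 3.3 | 2.927 | 2.64 | 0.018 | 0.0027 |

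The reported p < 0.01 for both contrasts is reproduced for a PE SD up to about 2.6. A PE SD of 3.3 contradicts it at 18 per arm and is left out below.

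**5. Differential error that would remove significance at 0.05** (difference minus critical difference).
- PE SD 1.7: 3.0 − 2.31 = 0.69 and 3.6 − 2.31 = 1.29 degrees.
- PE SD 2.62: 3.0 − 2.48 = 0.52 and 3.6 − 2.48 = 1.12 degrees.
- As shares of the effect: 0.52/3.0 = 17% to 0.69/3.0 = 23% for SMRS; 1.12/3.6 = 31% to 1.29/3.6 = 36% for SMRSS.

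**6. Sensitivity.**
- *Unequal arms.* Over all splits of the 72 completers within the randomised arm sizes (20/20/19/20) that keep both p < 0.01, with PE SD 1.7-3.3, the ranges are about 0.5-0.9 and 0.8-1.5 degrees.
- *Unadjusted Welch test, 18 per arm.* SE = √[(3.3² + 1.7²)/18] = 0.875 and √[(3.1² + 1.7²)/18] = 0.833. The lower 95% limits are 1.20 and 1.89 degrees.
- *Rounding.* Each mean is rounded to 0.1, so every margin carries about ±0.1 degree.

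**The case against.** - **The reading was not unchecked.** A second researcher watched each assessment and agreed to its accuracy, and could catch a grossly misplaced line. That stands, so a reader should not infer that any error would pass unseen. But the observer is unblinded and records no separate value, so a small, consistent lean could be agreed to in good faith.
- **It was not a single measurement.** Two measurements are averaged. That also stands: the weakness is one reader, not one reading.
- **The follow-up reader is not named.** That the investigator also read the follow-up images is inferred from the one reading procedure described. The point survives, because the non-blinding statement covers any researcher.
- **The tipping points measure fragility, not bias.** This is the strongest objection, and it is right. Any trial with small arms and six adjusted comparisons has a thin margin, whoever reads the images. The unadjusted margins (1.2 and 1.9 degrees) are wider, and the adjusted ones depend on unreported inputs. Nothing in the documents shows that 0.5 degree of differential error is plausible or implausible.
- **A tempting stronger reading is that the reported effects are artefacts of reading.** The documents do not support it: they give no reader error, and explaining the effects entirely would take 3.0 or 3.6 degrees in favour of exercise.
- **Re-reading repairs only line placement.** This stands and limits the remedy.

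**Conclusion.** The point holds as a weakness in how the outcome is measured, not as evidence that the result is wrong. CVA change carries the whole between-group comparison, the reader is unblinded, and the described check is neither masked nor independent. Differential follow-up reading error would pass straight into the group difference; whether it occurred, and its size, cannot be judged from the documents.

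The firmest size is the 3.0 or 3.6 degrees needed to explain the effects entirely. The margins of about 0.5-0.7 degrees (SMRS) and 1.1-1.3 degrees (SMRSS) rest on 18 completers per arm, a PE SD of 1.7-2.6, and p < 0.01 being the Gabriel p-value.

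This should be corrected, with medium confidence: a cheap improvement is available, provided the images still exist.

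**What to change.** **If the image files were kept:**
1. An existing team member other than the readers codes the images to hide identity, arm and visit, crops them while keeping the levelled orientation, and shuffles baseline and follow-up together.
2. The investigator and the second researcher, the two people already present at each reading, read every image separately without the code. This replaces watch-and-agree.
3. Use the mean masked reading as the outcome, show the result from the original readings beside it, and report inter-reader agreement.
4. Keep the original screening reading for eligibility, so that a re-read baseline above 53 degrees removes nobody.

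**Cost.** Assuming two photographs per visit, 72 × 4 = 288 images and 288 × 2 = 576 readings. At an assumed 1-2 minutes per reading this is 9.6-19.2 hours. Coding and cropping at an assumed 0.5-1 minute per image adds 2.4-4.8 hours. The total is about 12-24 staff hours, with no added readers or visits. Masking is imperfect if readers recognise participants, and neither image retention nor a free coder is documented.

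**If the images were not kept:** state as a limitation that CVA was read by a single unmasked reader (mean of two measurements) with no independent second reading.

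**In either case:** state that masked re-reading cannot correct arm-dependent differences at image capture, whether from unblinded participants' posture or from unblinded staff seating, positioning or instructing them.
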